### 12.4 Visit 3 (Day 2 [24 h $\pm$ 2 h.]) MAD Treatment

Patients will return after the Single Ascending Dose Treatment. Patient disease assessments will be performed as specified in the schedule of events table.

- Vital signs (blood pressure, heart rate, temperature) will be examined within 10 minutes prior to the start of treatment
- Baseline Patient Disease Assessment: Visual examination of chronic ulcer, score target ulcer using DUSS Scoring System, Swab wound to culture for microbiological examination
- Photo Documentation and Calculation of the Ulcer Area and Depth using the Aranz Medical SilhouetteTM System

The Principal Investigator will visually exam the chronic ulcer to determine if a patient is eligible to continue in the study. Eligible patients will be provided with his/her designated test product kit and instructed to apply the product twice daily for one (1) week (7 days). Test product application will be demonstrated, and patient instruction sheet reviewed, using the assigned test product. The patients will be observed applying the first dose in the clinic to ensure compliance (administering Test Product to the infected diabetic foot ulcer and surrounding intact skin at a dose of 1 to 3 drops from a dropper bottle per 1 cm^2 of ulcer area, left open to air for 5 minutes and then dressed using Owens gauge, Kerlex and tape.). The patient will be scheduled for the next follow-up visit, with a reminder to bring the test article kit to the visit.

### 12.5 Visit 4 (Day 9 + 1) Follow-Up to 7 Twice Daily Treatments

The study patient will return for a follow-up evaluation to the clinical site on Day 9 + 1. At this follow-up visit, the patient will undergo the following procedures and evaluations.

- Vital signs measurements including weight, temperature, resting blood pressure, heart rate, and respiratory rate
- Baseline laboratory tests (blood chemistries and hematology)
- Visual examination of the ulcer
- Scoring of the Ulcer(s) using the DUSS and DFI Wound n System
- Photo Documentation and Calculation of the Ulcer Area and Depth using the Aranz Medical SilhouetteTM System
- Collection of a sample from the ulcer for microbiological assessment
- Collection of Subject Home Treatment Log
- Collection of Investigational Product (IP)

Patients will be given a 7 day supply of non-abrasive bandage and written instructions on the proper care and hygiene to include keeping the ulcer clean and bandage dry until the Day 15 follow up visit. In addition, patients will be told to call if there is any worsening of the ulcer with regard to pain, infection, or swelling.

### 12.6 Visit 5 (Day 15 $\pm$ 1) End of Study (EOS) Visit

The patient shall attend final end-of-study visit  $15 \pm 1$  days after receiving Test Product. At this follow-up visit, the patient will undergo the following procedures and evaluations.

- Vital signs measurements including weight, temperature, resting blood pressure, heart rate, and respiratory rate
- Physcial examination
- Baseline laboratory tests (blood chemistries and hematology)
- Visual examination of the ulcer
- Scoring of the Ulcer(s) using the DUSS and DFI Wound Scoring System
- Photo Documentation and Calculation of the Ulcer Area and Depth using the Aranz Medical SilhouetteTM System

Collection of a sample from the ulcer for microbiological assessment

### 12.7 At Every Visit

All adverse events (local and systemic), concurrent procedures, and changes in concomitant medications during the study will be recorded on the source documents and case report forms (CRFs). Local reactions to test product administration include but are not limited to pain, edema, rash, cellulitis, localized infectious processes, and any systemic reaction including fever, allergic reaction, and anaphylaxis.

### 12.8 Early Termination Visit

If a subject withdraws prior to completing the study, the reason for withdrawal will be documented. If a subject withdraws early due to an adverse event, he/she will be followed until resolution/stabilization of the adverse event.

If a subject prematurely withdraws from the study they will be asked to complete the study procedures and evaluations performed in the final study visit at the time of withdrawal from the study:

- Vital signs measurements including weight, temperature, resting blood pressure, heart rate, and respiratory rate
- Physcial examination
- Baseline laboratory tests (blood chemistries and hematology)
- Visual examination of the ulcer
- Scoring of the Ulcer(s) using the DUSS System

### 12.9 Adverse Event Monitoring

Subjects will be monitored for any adverse events throughout the screening and until the end-of-study visit on Day 15. Adverse events will be specifically assessed by observation at Day 1 following administration of the first dose of investigational product, at Day 2 following the second dose administration, at Day 9 visit and at Day 15 visit. Abnormal and clinically significant measurements obtained from the local lab will be used to note adverse events.

Vital signs (blood pressure and heart rate) can be monitored per hospital/site protocol following administration of the first dose of investigational product, and at Day 2 following the second dose administration. Deviations from normal will be recorded as adverse events.

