#### **Study Design**

Multi center, Randomized Double Blind, Placebo-Controlled, Dose Escalating Study

Clinical investigation Objective(s) and Endpoint:

	Objective	Endpoint	Variable
Primary	To assess the safety and tolerability of escalating doses of topically applied bisphosphocin™ Nu-3	Treatment emergent events related to clinical investigation product	
 
Vital signs,
 
CBC analysis, CMP analysis,
 
Physical examination,
 

Secondary	• To assess the clinical and microbiological response to bisphosphocin™ Nu-3	

Reduction of pathogenic bacteria

Visual evaluation of the ulcer

	

Aerobic and anaerobic culture and sensitivity

DUSS Score

	• To support determination of the appropriate dose range of Nu-3 to be employed in future clinical studies.		

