## 13.3 Clinical chemistry

A CMP (biochemistry and hematology) will be performed by the local lab at screening, and then repeated at Day 9 and Day 15 after the first dosing. Changes from baseline will be assessed as a safety parameter. If a change in a clinical chemistry parameter is observed and considered to be clinically significant by the investigator, the observation will be written up as an adverse event.

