**Probable** - An event that follows a reasonable temporal sequence from administration of the test article; that follows a known or expected response pattern to the test article; and that is confirmed by improvement on stopping or reducing the dosage of the test article; and that is unlikely to have been caused by concurrent/underlying illness or other drugs, procedures, or other causes.

**Possible** - An event that follows a reasonable temporal sequence from administration of the test article; that follows a known or expected response pattern to the test article; but may have been caused by concurrent/underlying illness, other drug, procedure, or other causes.

**Unlikely** - An event that does not follow a reasonable temporal sequence from administration of the test article; that does not follow a known or expected response pattern to the test article, or most likely was caused by concurrent/underlying illness, other drug, procedure, or other causes, because of their known effects.

**Not Related** - An event almost certainly caused by concurrent/underlying illness, other drug, procedure, or other causes.

An **adverse reaction** is any AE caused by a drug. Adverse reactions are a subset of all suspected adverse reactions for which there is reason to conclude that the drug caused the event. For the purposes of prescription drug labelling, the term adverse reaction means an undesirable effect, reasonably associated with the use of a drug that may occur as part of its pharmacological action or may be unpredictable in its occurrence.

A **suspected adverse reaction** is any adverse event for which there is a reasonable possibility that the drug caused the event.

For the purposes of safety reporting, "reasonable possibility" means there is evidence to suggest a causal relationship between the drug and the adverse event. A suspected adverse reaction implies a lesser degree of certainty about causality than adverse reaction, which means any adverse event caused by a drug.

An event that is a **serious adverse event (SAE)** must be recorded on the AE eCRF and requires expeditious handling to comply with regulatory requirements.

An adverse event or suspected adverse reaction is considered "serious" if, in the opinion of either the investigator or sponsor, it results in any of the following outcomes:

- Death.
- Life-threatening event.
- Inpatient hospitalization or prolongation of existing hospitalization.

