## DEFINITIONS

|  |   |
|--|---|
| Intent-to-Treat (ITT) Population         | Includes all randomized subjects.   |
| Safety Population                        | Includes all subjects administered any amount of the study drug.  |
| Per-Protocol (PP) Population             | Includes all randomized subjects who received all doses of the of investigational product as required by the protocol and had no major protocol violations. |
| Treatment-emergent Adverse Events (TEAE) | AEs with an onset time after dosing and pre-existing AEs that worsen during the study.  |

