### **9.1 Adverse Events**

All AE summaries will be restricted to Treatment-Emergent Adverse Events (TEAE), which are

defined as those AEs that occurred after dosing and those pre-existing AEs that worsened during the study. Verbatim terms on case report forms will be mapped to preferred terms and system organ classes using the MedDRA dictionary (version 14.1).

Each AE summary will be displayed by dose group. Summaries that are displayed by system organ class and preferred terms will be ordered by descending order of incidence of system organ class and preferred term within each system organ class. Summaries of the following types will be presented:

- Subject incidence of TEAEs and total number of unique TEAEs by MedDRA system organ class and preferred term.
- Subject incidence of TEAEs by MedDRA system organ class, preferred term, and highest severity. At each level of subject summarization, a subject is classified according to the highest severity if the subject reported one or more events. An event with missing severity will not be imputed.
- Subject incidence of TEAEs by MedDRA system organ class, preferred term, and closest relationship to study drug (Not Related, Unlikely, Possibly, Probable, Definite). At each level of subject summarization, a subject is classified according to the closest relationship if the subject reported one or more events. AEs with a missing relationship will be considered definite related for this summary.
- Subject incidence of serious TEAEs and total number of unique serious TEAEs by MedDRA system organ class and preferred term.

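### Protocol 12.9 makes any post-dose blood pressure or heart rate value outside an undefined normal an adverse event, without the test applied to laboratory values

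*Protocol*

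**What the plan says.** **Vital signs.** Protocol 12.9 sets the scope: "Vital signs (blood pressure and heart rate) can be monitored per hospital/site protocol following administration of the first dose of investigational product", and likewise after the second dose on Day 2. The next sentence is the rule: "Deviations from normal will be recorded as adverse events". No normal range is given, and there is no reference to the pre-dose value or to clinical significance.

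**Laboratory values.** The preceding paragraph of 12.9 is stricter: "Abnormal and clinically significant measurements obtained from the local lab will be used to note adverse events". Protocol 13.3 is stricter still. It starts from an observed change in a parameter and requires that the change be "considered to be clinically significant by the investigator, the observation will be written up as an adverse event".

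**Treatment emergence.** The SAP definitions count "AEs with an onset time after dosing and pre-existing AEs that worsen during the study". SAP 9.1 restricts all adverse event summaries to TEAEs, "defined as those AEs that occurred after dosing and those pre-existing AEs that worsened during the study".

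**Primary endpoint and causality.** The Synopsis gives the primary endpoint as "Treatment emergent events related to clinical investigation product". Protocol 13.4 requires a relationship rating for each event and defines Not Related as "An event almost certainly caused by concurrent/underlying illness, other drug, procedure, or other causes". SAP 9.1 counts a missing relationship as definite in the relationship table.

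**The concern.** The vital-sign rule is mandatory once a reading exists, and it lacks the filter that the same section applies to laboratory results. Eligibility runs to age 85 in people with diabetes, and Protocol 9.1.2 sets no blood pressure or heart rate limit. Some subjects may therefore be outside normal before their first dose. Followed literally, the rule turns their usual readings into adverse events with a post-dose onset.

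What is at stake is how readable the all-cause safety tables are. Dose groups have 8 subjects, and the placebo subjects (2 per cohort) are pooled, so a few background entries change the displayed incidence noticeably. Monitoring follows site practice, so the number of readings and the meaning of normal can also differ between sites. Because cohorts are sequential, a shift in site mix could produce differences between dose groups that have nothing to do with the drug.

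**Working it through.** The plan states no figure on this point and, by Protocol 16.1 and SAP 10, no sample size was calculated. There is nothing to reproduce. The check is first textual, then an illustration on stated assumptions.

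**1. The three recording rules side by side**

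| Rule | Change from earlier value needed? | Clinical significance needed? |
|---|---|---|
| 12.9, laboratory | No (abnormal value) | Yes |
| 13.3, laboratory | Yes | Yes |
| 12.9, blood pressure and heart rate | No | No |

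**2. Does anything else remove a standing abnormality?**

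- Protocol 13.4 defines an adverse event broadly, with no exclusion for unworsened pre-existing conditions. The three-cohort protocol text bound in the same document has such an exclusion (6.2.1) and ties abnormal vital signs to signs or symptoms (6.2.4). The five-cohort text carries neither.
- Protocol 12.2 records past history only where the investigator thinks it relevant to the current diagnosis, so long-standing hypertension may not be on record.
- The SAP's worsening clause applies to pre-existing adverse events. A high pressure first logged at a post-dose reading was not previously an adverse event and has its onset after dosing, so the clause does not reliably remove it.

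**3. Where the entry goes.** Of the four SAP adverse event tables (14.3.1.1 to 14.3.1.4), only 14.3.1.3 splits by relationship. A non-serious background entry therefore counts in the overall and severity tables whatever its causality rating.

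**4. Illustration of size in the all-cause tables.** Let p be the share of subjects with at least one out-of-range post-dose blood pressure or heart rate. It is assumed to be 10% to 70%, with every subject monitored and subjects independent. The expected number is n × p, and the chance of at least one in a dose group of 8 is 1 − (1 − p)^8. The 50 subjects are those of the five-cohort protocol.

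| p | Expected of 8 | P(at least one of 8) | Expected of 10 placebo | Expected of 50 |
|---|---|---|---|---|
| 0.1 | 0.8 | 0.57 | 1 | 5 |
| 0.3 | 2.4 | 0.94 | 3 | 15 |
| 0.5 | 4.0 | 0.996 | 5 | 25 |
| 0.7 | 5.6 | >0.999 | 7 | 35 |

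The SAP plans three cohorts of 10. For 30 subjects the last column becomes 3, 9, 15 and 21.

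**5. Illustration of leakage into product-related events.** If 5% to 20% of such entries were rated at least possibly related (assumed), the expected number among 40 Nu-3 subjects is 40 × p × share. At p = 0.3 this is 0.6 to 2.4, and at p = 0.5 it is 1 to 4.

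**6. Effect of requiring a change.** If 10% to 25% of out-of-range subjects had worsened from the pre-dose value (assumed), the entries among 50 subjects fall from 15 to 1.5–3.75 at p = 0.3, and from 25 to 2.5–6.25 at p = 0.5. The clinical-significance test would lower these further.

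**The case against.** A fair defence has four parts.

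- **Scope.** The sentence covers two parameters after two dosing occasions, and the monitoring is optional. It does not name temperature, respiratory rate, Day 9 or Day 15. This stands: a reader might infer that every vital-sign deviation in the study becomes an adverse event, but the text does not say so.
- **Primary endpoint.** A reader might infer that background hypertension fills the primary safety endpoint. The documents do not support that. The endpoint is limited to product-related events, and unworsened underlying illness belongs under Not Related. Two routes remain: a wrong causality rating, and a missing one, which SAP 9.1 counts as definite. A dilution calculation that treats each background entry as a primary endpoint event would measure the wrong quantity on assumed inputs.
- **Masking.** TEAEs are tabulated by preferred term, so blood pressure and heart rate entries can be told apart from local ulcer reactions. SAP 4 confines between-group testing to efficacy parameters, so no planned SAP safety test loses power. This stands, although Protocol 16 still speaks of comparing all parameters with placebo.
- **Dose-limiting toxicity.** A reader might infer that background readings would drive escalation decisions. Protocol 8.10.5.2 requires Grade 2 or higher and at least a possible relationship. Under 13.4, possible requires a known or expected response pattern to the test article. The route exists but is narrow, and nothing in the documents sizes it.

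It can also be argued that recording broadly and sorting later by grade and causality suits a first-in-human study. That is defensible as a policy, but it does not explain the different standard for laboratory values or the absence of a definition of normal.

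**Conclusion.** The point holds as a recording inconsistency that can inflate the all-cause TEAE tables. As written, 12.9 admits standing blood pressure and heart rate abnormalities as adverse events, and the SAP definition of treatment emergence does not reliably take them out. The possible size ranges from under one to more than half of an 8-subject dose group, and it rests entirely on the assumed 10% to 70% prevalence and on monitoring being done. The effect on the product-related primary endpoint is confined to misattributed or missing causality and cannot be derived from the documents. This is an inexpensive improvement to the wording and does not show that the primary endpoint is compromised.

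**What to change.** - **Protocol 12.9.** Replace the sentence so that a post-dose blood pressure or heart rate finding is recorded as an adverse event when it is a change from the pre-dose value that the investigator considers clinically significant, as 13.3 does for laboratory values. The comparison value already exists: 12.3 schedules vital signs within 10 minutes before treatment, and SAP 9.2 defines baseline as the last value before study drug.
- **SAP 9.2, heart rate.** Add low-value and decrease cut-offs to the outlier table. It now has only values above 120 or 130 bpm and increases of at least 20 or 30 bpm, so a low heart rate judged not significant would appear in neither the adverse event tables nor the outlier table.
- **SAP 9.2, coverage.** State that the optional post-dose readings are included in the change-from-baseline summary, which is organised by scheduled visit. With listing 16.2.13.1, all recorded readings then stay visible.

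The cost is one protocol sentence and a few SAP lines. The downside is reliance on investigator judgement, which the protocol already accepts for laboratory values.

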#### 13 ASSESSMENT OF SAFETY

### 13.1 Physical Examination

Physical examinations are performed at screening and at the Day 15 End of Study Visit. The examinations will include general appearance, skin, neck, eyes, ears, nose, throat, heart, lungs, abdomen, cervical and axillary lymph nodes, extremities, and nervous system. Height is measured in stocking or bare feet, and recorded in inches, at screening. Weight is recorded in pounds at screening and Day 15 visit.

### 13.2 Vital Signs

Vital Signs, including one or more of systolic and diastolic blood pressure, pulse, and temperature, are recorded at screening, at Day 1 visit, at Day 2 visit, at Day 9 visit, and at the Day 15 Final Visit. See Schedule of Events for detail.

Consistent BP measurement in one arm is preferred to facilitate comparisons of serial BP measurements. However, optimal performance of other procedures (e.g., blood sampling) may require changing BP measurement from one arm to the other.

The investigator or designee will perform a thorough physical examination at the start of the study and brief physical examination at 15 days post dose administration. Any changes in the overall health and well-being of the subject during the study will be reported as an adverse event. If the subject is unable to return for the 15 day visit, then the physical exam is not mandatory. In this case, the subject's well-being may be assessed by phone.

An investigator will be in the premises during the investigational product administration and on call until the end of the study.

## 13.3 Clinical chemistry

A CMP (biochemistry and hematology) will be performed by the local lab at screening, and then repeated at Day 9 and Day 15 after the first dosing. Changes from baseline will be assessed as a safety parameter. If a change in a clinical chemistry parameter is observed and considered to be clinically significant by the investigator, the observation will be written up as an adverse event.

### 13.4 Adverse events

Subjects will be monitored for any adverse events throughout the screening and until the end-of-study visit on day 15. Adverse events will be specifically assessed by observation at Day 1 following administration of the first dose of investigational product, at Day 2 following the second dose administration, at Day 9 visit and at Day 15 visit.

The recording of adverse events is an important aspect of study documentation. It is of utmost importance that all staff members at the site involved in the study are familiar with the content of this section in order to document all adverse events according to the detailed guidelines set out below. During the study where there is safety evaluation, the principal investigator or site staff will be responsible for detecting, documenting and reporting AEs and SAEs.

An **adverse event (AE)** is any untoward medical occurrence associated with the use of a drug in humans, whether or not considered drug related. Events that are expected as a result of a procedure (other than drug administration of investigational product) that the subject undergoes should not be listed as an AE unless the event is more severe than expected or deemed significant by the Principal Investigator.

Timely and complete reporting of all AEs assists the medical staff and sponsor in identifying any untoward medical occurrence, thereby allowing:

- 1. protection of the safety of study subjects;
- 2. a greater understanding of the overall safety profile of the test article;
- 3. recognition of dose-related test article toxicity;
- 4. appropriate modification of study protocols;
- 5. improvements in study design or procedures; and
- 6. adherence to worldwide regulatory requirements.

Test article is defined as a pharmaceutical form of an active ingredient (or "primary operational component" for devices) or vehicle/placebo being tested or used as a reference in

the study, whether blinded or unblinded. AEs may be either spontaneously reported or elicited during questioning and examination of a subject. All AEs must be completely recorded on the within the electronic source document system. If known, the Investigator should report the diagnosis of the underlying illness or disorder, rather than its individual symptoms. Subjects experiencing AEs that cause interruption or discontinuation of test article, or those experiencing AEs that are present at the end of their participation in the study will receive follow-up as appropriate. If possible, report the outcome of any AE that caused permanent discontinuation or that was present at the end of the study particularly if the AE was considered by the investigator to be definitely, probably, or possibly related to test article.

The investigator will instruct the subject to report any adverse events that may occur during the study. At each visit, the investigator will ask the subject, in non-directive fashion, about any change in the subject's overall condition since the previous visit.

The severity of each adverse event, as judged by the Investigator, will be graded according to Common Terminology Criteria for Adverse Events v4.02 (CTCAE). For AEs not listed in the CTCAE table, the severity of adverse changes in physical signs or symptoms will be classified as follows (consistent with CTCAE):

**Grade 1 Mild** - asymptomatic or mild symptoms; clinical or diagnostic observations only; intervention not indicated.

**Grade 2 Moderate** - minimal, local or noninvasive intervention indicated; limiting age-appropriate instrumental activities of daily living.

**Grade 3 Severe** - medically significant but not immediately life-threatening; hospitalization or prolongation of hospitalization indicated; disabling; limiting self-care activities of daily living.

Grade 4 Life-threatening - urgent intervention indicated.

Grade 5 Death - Death related to AE.

The investigator must determine the relationship of the AE to the test article according to the following categories:

**Definite** - An event that follows a reasonable temporal sequence from administration of the test article; that follows a known or expected response pattern to the test article; and that is confirmed by improvement on stopping or reducing the dosage, and reappearance of the event on repeated exposure (re-challenge).

**Probable** - An event that follows a reasonable temporal sequence from administration of the test article; that follows a known or expected response pattern to the test article; and that is confirmed by improvement on stopping or reducing the dosage of the test article; and that is unlikely to have been caused by concurrent/underlying illness or other drugs, procedures, or other causes.

**Possible** - An event that follows a reasonable temporal sequence from administration of the test article; that follows a known or expected response pattern to the test article; but may have been caused by concurrent/underlying illness, other drug, procedure, or other causes.

**Unlikely** - An event that does not follow a reasonable temporal sequence from administration of the test article; that does not follow a known or expected response pattern to the test article, or most likely was caused by concurrent/underlying illness, other drug, procedure, or other causes, because of their known effects.

**Not Related** - An event almost certainly caused by concurrent/underlying illness, other drug, procedure, or other causes.

An **adverse reaction** is any AE caused by a drug. Adverse reactions are a subset of all suspected adverse reactions for which there is reason to conclude that the drug caused the event. For the purposes of prescription drug labelling, the term adverse reaction means an undesirable effect, reasonably associated with the use of a drug that may occur as part of its pharmacological action or may be unpredictable in its occurrence.

A **suspected adverse reaction** is any adverse event for which there is a reasonable possibility that the drug caused the event.

For the purposes of safety reporting, "reasonable possibility" means there is evidence to suggest a causal relationship between the drug and the adverse event. A suspected adverse reaction implies a lesser degree of certainty about causality than adverse reaction, which means any adverse event caused by a drug.

An event that is a **serious adverse event (SAE)** must be recorded on the AE eCRF and requires expeditious handling to comply with regulatory requirements.

An adverse event or suspected adverse reaction is considered "serious" if, in the opinion of either the investigator or sponsor, it results in any of the following outcomes:

- Death.
- Life-threatening event.
- Inpatient hospitalization or prolongation of existing hospitalization.
- Persistent or significant incapacity or substantial disruption of the ability to conduct normal life functions.
- Congenital anomaly/birth defect.
- Is an important medical event defined as a medical event(s) that may not result in death, be life-threatening, or require hospitalization but, based upon appropriate medical judgment, may jeopardize the patient/subject and may require medical or surgical intervention to prevent one of the outcomes listed in the definition above. Examples of such medical events include allergic bronchospasm requiring intensive treatment in an emergency room or at home, blood dyscrasias or convulsions that do not result in inpatient hospitalization, or the development of drug dependency or drug abuse.

Events NOT considered to be SAEs are:

- Hospitalizations for the treatment, which was elective or pre-planned, of a pre-existing condition that did not worsen. A hospitalization planned after the index admission, such as a staged PCI procedure, or a planned prolonged hospitalization, such as coronary artery bypass surgery related to the index admission, will not be considered an SAE.
- Treatment on an emergency, outpatient basis, for an event not fulfilling any of the definitions of "serious" given above and not resulting in hospital admission.

The Medical Monitor, Lead Principal Investigator, or Sponsor may be consulted with any questions regarding the definition of "planned". The Medical Monitor may be consulted regarding other questions about SAEs.

Adverse events classified as "serious" require expeditious handling and reporting to the Medical Monitor, Safety Officer or designee to comply with regulatory requirements. All SAEs, whether related or unrelated to test article, must be immediately reported by telephone to the Medical Monitor, Safety Officer or, in the event that neither is available, to the Project Manager listed on the first page of the protocol. All SAEs should be entered in the eCRF as soon as possible. These include those SAEs listed in the protocol or Investigator Brochure and must include an assessment of whether there is a reasonable possibility that the drug caused the event.

All SAE are required to be captured on the study supplied SAE report form. Please contact the Safety Officer at

If only limited information is initially available, follow-up reports are required. In the event of death, if an autopsy is performed, a copy of the report should be sent to the Sponsor or designee, if available.

As required, the Sponsor or designee will notify participating investigators of all suspected adverse reactions that are serious and unexpected. This notification will be in the form of an IND safety report of potential serious risks as soon as possible but no later than 15 calendar days after the Sponsor determines that the information is "reportable" according to the criteria listed in Section 312.32(c)(1)(i) to (iv) of the CFRs. These are:

- Serious and unexpected suspected adverse reactions,
- Findings from other studies including epidemiological studies, pooled analyses or other clinical studies that suggest a significant risk in humans exposed to the test articles,
- Findings from animal or in vitro tests that suggest a significant risk to humans exposed to the test articles, or reports of significant organ toxicity at or near the expected human exposure, and
- Clinically important increases in the rate of occurrence of serious suspected adverse reactions.

Upon receiving such notices, the investigator must review and retain the notice with the Investigator Brochure and immediately submit a copy of this information to the responsible IRB according to local regulations. The investigator and IRB will determine if the ICF requires revision. The investigator should also comply with the IRB procedures for reporting any other safety information. Where required, submission of safety updates by the investigator to Health Authorities should be handled according to local regulations.

All AEs must be recorded on the AE CRF. AEs should be followed to resolution or stabilization (if possible), and reported as SAEs if they become serious. AEs will be collected starting when the subject signs the ICF and ending with the end-of-study visit on Day 15. For subjects who withdraw from the study, the collection of AEs will end 15 days after the first dose administration. If any adverse event is present when a subject completes the study or if a

subject is withdrawn from the study and the adverse event has still not resolved at this time, additional follow-up will be performed, as appropriate. The investigator will continue to follow-up all serious adverse events or other adverse events that are considered to be related to the investigational products, until it is resolved or assessed to be stable by the Investigator. This follow-up may be extended beyond the end of the study period. An adverse event can reach one of the following outcomes:

- Completely recovered from the AE
- Recovered with sequelae
- Ongoing
- Ongoing at the time of death
- Death
- Unknown

